4.1.1 Stage I

Approximately 1990 female participants 9 to 45 years of age who meet eligibility will be enrolled in the study. Enrollment of participants will be stratified based on the following age strata: 9-19 years old (N=690), 20-26 years old (N=650), and 27-45 years old (N=650). Within each 9-19 years old group and 27-45 years old group, enrollment will be further stratified by the pre-defined age subgroups as described in Section 6.3.1.1.

For participants 9-15 years of age, a sequential enrollment will be applied. The 1st step is to enroll 25 participants 9-15 years of age and the safety data after Dose 1 through Day 15 post Dose 2 will be reviewed by a Data Monitoring Committee (DMC). If the safety data are judged to be acceptable in the opinion of the DMC, then the 25 participants 9 to 15 years of age enrolled initially will receive a 3rd dose at Visit 8, and the enrollment will be initiated to the rest of participants 9-15 years of age. All participants 9 to 15 years of age enrolled in the 2nd step of enrollment will receive one dose of 9vHPV vaccine at Visit 1, Visit 4, and Visit 8, respectively.

The enrollment of participants 16 to 45 years of age will be initiated at the same time as that of the first 25 participants 9-15 years of age. Safety review by the DMC is not necessary for participants 16 to 45 years of age. All enrolled participants 16 to 45 years of age will receive one dose of 9vHPV vaccine at Visit 1, Visit 4, and Visit 8, respectively.

Medical history and vital signs will be collected at Day 1 for all participants. Physical examination will be conducted at Day 1 for all participants, and at Visit 6 for the 25 participants initially enrolled in the 9-15 years old group for whom the safety will be reviewed by the DMC.

Serum samples will be obtained from each participant at Day 1 prior to vaccination and 1 month post Dose 3 (Visit 10) for measurement of anti-HPV antibodies for HPV 6, 11, 16, 18,

31, 33, 45, 52, and 58 by cLIA and IgG LIA. However, only serum samples from a subset of participants will be tested by PBNA (N=600 in total, i.e. 200 participants randomly selected from each age group) as an exploratory objective of this study.

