where p_1 is the proportion of participants who seroconvert by 1 month post Dose 3 in the 27-45 years old group and p_2 is the proportion of participants who seroconvert by 1 month post dose 3 in the 20-26 years old group.

The tests above will be conducted using the method of Miettinen and Nurminen [Miettinen, O. and Nurminen, M. 1985]. The statistical criterion for non-inferiority requires that the lower bound of two-sided 97.5% confidence interval for the difference (27-45 years of age minus 20-26 years of age) in seroconversion percentages being greater than -5 percentage points for each HPV type.

Anti-HPV GMTs and seroconversion percentages measured by IgG LIA will be summarized as secondary objective of immunogenicity.

PBNA results (GMTs and seroconversion percentages) will be summarized as exploratory objective and will be provided in a supplemental report after the data are available.

The extended visit window of study vaccination may result in different intervals between doses, which has real potential to alter the read-out of the anti-HPV titers compared to the read-out expected from the original designated regimen (0, 2, 6 months). Besides, It is not

guaranteed that the effect that the time interval between doses will have on anti-HPV titer read-outs will be the same in each of the age groups. There is a real possibility that the variability of anti-HPV titers in each age group will affect the resulting GMTs in each age group in a way that the resulting GMT ratio is now different from the assumed GMT ratio used to power the non-inferiority hypothesis testing. If the shift in GMT ratio is in the direction greater than 1.0, the altered time interval between doses biased the hypothesis testing in favor of the age group represented by the numerator of the GMT ratio (i.e. 9-19 years old or 27-45 years old group). If the shift in GMT ratio is in the direction less than 1.0, then there is a risk that the hypothesis test will become underpowered. And the other situation would be no meaningful shift in the GMT ratio between age groups. So to investigate the potential impact, a supportive analysis on PPI population will be performed by HPV type using the following stepwise regression models.

- Step 1: A no-intercept regression model will be fitted on the natural logarithm of anti-HPV cLIA titers at 1 month post dose 3 (as dependent variable Y) with the following independent variables:

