 - X1: Indicator for 9-19 years of age (X1=1 if 9-19 year-old, X1=0 if otherwise)
 - X2: Indicator for 20-26 years of age (X2=1 if 20-26 year-old, X2=0 if otherwise)
 - X3: Indicator for 27-45 years of age (X3=1 if 27-45 year-old; X3=0 if otherwise)
 - X4: Time (in months) from Dose 1 to Dose 2
 - X5: Time (in months) from Dose 2 to Dose 3
- The regression coefficients associated with X1, X2, and X3 represent the expected GMTs in natural logarithm scale (or log-GMT) in each of the 3 age groups.
- The regression coefficients associated with X4 and X5 represents the contribution of time interval between vaccinations on the expected log-GMTs.
- The association of log-GMT with X4 and X5, in addition to (or over and above) the association of log-GMT with the protocol-specified age groupings will be evaluated as follows:
 - The partial correlation coefficient associated with X4 and X5, given X1, X2, and X3 are already in the model, will be calculated and provided.
 - The nominal statistical significance of X4 and X5, given X1, X2, and X3 are already in the model, will be evaluated.
 - If X4 and X5 are nominally statistically significant ($p\text{-value} \leq 0.05$), Step 2 outlined below will be performed.

- If X4 and X5 are not nominally statistically significant ($p\text{-value} > 0.05$), Step 2 outlined below will not be performed, and is an indication that there is no association between dosing interval and expected log-GMT. Step 2: The following explanatory variables will be added to the regression model specified in Step 1:
 - X1*X4: Time (in months) from Dose 1 to Dose 2 among 9-19 year-olds
 - X3*X4: Time (in months) from Dose 1 to Dose 2 among 27-45 year-olds
 - X1*X5: Time (in months) from Dose 2 to Dose 3 among 9-19 year-olds
 - X3*X5: Time (in months) from Dose 2 to Dose 3 among 27-45 year-olds
- These 4 explanatory variables provide insight on whether the effect of dosing interval varies by age group.
- The association of log-GMT with X1*X4, X3*X4, X1*X5, and X3*X5, in addition to (or over and above) the association of log-GMT with the protocol-specified age groupings and dosing intervals, will be evaluated as follows:
 - The partial correlation coefficient associated with X1*X4, X3*X4, X1*X5, and X3*X5, given X1, X2, X3, X4, and X5 are already in the model, will be calculated and provided.
 - The nominal statistical significance of X1*X4, X3*X4, X1*X5, and X3*X5, given X1, X2, X3, X4, and X5 are already in the model, will be evaluated.

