9.8 Multiplicity

Figure 2 shows the multiplicity strategy for the study.

[figure not shown]

Figure 2 Multiple Strategies to Control Overall Type One Error Rate

For the dual-primary hypotheses (H1 and H2), Bonferroni method is used to control overall one-sided type I error at level of 0.025. Each of the dual-primary hypotheses has a 0.0125 one-sided type I error. The study would be successful if either H1 or H2 are met. If H1 is not met then no further testing (H3, H4) will be completed.

Fix sequence testing strategy is used to control multiplicity between dual-primary hypothesis (H1) and secondary hypotheses (H3 and H4). The testing order is as follows: H1 (GMT, 9-19yr vs.20-26yr) will be tested firstly and if H1 wins H3 (seroconversion percentages, 9-19yr vs. 20-26yr) will then be tested; if H3 wins H4 (GMT, 9-15yr vs. 20-26yr) will be tested. Each one will be tested at a level of 0.0125. If anyone failed to reject null the subsequent ones would not be tested.

Furthermore, success is required on all 9 HPV types for hypotheses testing GMT and seroconversion percentages, so no multiplicity adjustment is needed to account for the multiple HPV types.

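### The dosing-interval regression pools ages 9-15 with 16-19, so H4 has no interval-adjusted contrast and the interval slopes can be biased if the two strata differ in both titre and dose spacing

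*Combined protocol and SAP*

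**What the plan says.** Section 9.6.1 explains that the extended vaccination windows could move the GMT ratio away from the value assumed for power, in either direction. It names the numerator groups at issue: "i.e. 9-19 years old or 27-45 years old group". The 9-15 group, which is the numerator of H4, is not named.

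The regression is run by HPV type on the PPI population. Step 1 has no intercept, three age indicators (X1 for 9-19, X2 for 20-26, X3 for 27-45) and two dose intervals in months (X4, Dose 1 to 2; X5, Dose 2 to 3). X1 is defined as "X1: Indicator for 9-19 years of age (X1=1 if 9-19 year-old, X1=0 if otherwise". Step 2 follows only on a condition: "If X4 and X5 are nominally statistically significant". Otherwise the plan takes the result as a sign of no association between dosing interval and titre. The Step 2 interactions use X1 and X3 only, for example "X1*X4: Time (in months) from Dose 1 to Dose 2 among 9-19 year-olds".

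In Section 9.8, H4 is the last step of the fixed sequence: "if H3 wins H4 (GMT, 9-15yr vs. 20-26yr) will be tested". On alpha it says: "Each one will be tested at a level of 0.0125". Section 6.3.1.1 makes 9-15 and 16-19 separate enrolment strata (about 2:1), and 27-35 and 36-45 likewise (about 1:1). Section 4.1.1 says: "For participants 9-15 years of age, a sequential enrollment will be applied".

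**The concern.** The reason given for the regression applies to any GMT-ratio non-inferiority test, and H4 is one, with margin 0.67. Yet no coefficient isolates 9-15. By contrast, 27-45 has its own indicator and interactions, although its GMT is only summarised and not tested. Table 3 lists one interval analysis and none for 9-15. Section 9.10 says 9-15 will be analysed for the secondary objectives but does not extend the regression to it, and Section 9.11 only describes intervals by histogram.

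There is a second, conditional problem. With one indicator for two strata, part of any titre difference between them goes into the interval slope whenever the strata also differ in mean interval. Step 1 could then open Step 2 for no reason, or close it and be read as evidence of no interval effect.

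What is at stake is how well the H4 result can be defended if intervals turn out uneven. Sections 2.1 and 4.1 say the Stage I data are to support extending the indication to 9-15 as well as to 27-45.

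**Working it through.** **Inputs from Section 9.9.1.** SD of ln titre 1.2; exclusions 15% (9-15 and 9-19) and 30% (20-26 and 27-45). Effective numbers: 460 × 0.85 = 391 (9-15); 230 × 0.85 = 195.5, taken as 195 (16-19); 650 × 0.70 = 455 in each older group. Total N = 1496. The 9-15 share of X1 is 391/586 = 0.67.

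**The plan's own figure.** For H4, SE = 1.2 × √(1/391 + 1/455) = 0.0828 and −ln 0.67 = 0.4005, so the noncentrality is 4.84. At one-sided 0.0125 the power is 0.9952 per type, and 0.9952^9 = 0.958. This matches Table 7 (0.995 and 0.958). The interval regression has no stated power.

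**Assumptions, not in the documents.** 9-15 to 16-19 GMT ratio 1.2 to 1.5; difference d in mean Dose 2-3 interval 0.5 or 1 month; within-stratum interval SD s of 0.6 or 1.0 month.

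**Bias of the X5 slope under the planned coding.** Let δ = ln(GMT ratio), q = 391 × 195/586 = 130.1 and SSx = 1496 × s². Then

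bias = δ·d·q / (SSx + d²·q), with SE ≈ 1.2 / √(SSx + d²·q).

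The bias is zero if δ = 0 or d = 0. With z = bias/SE, the false-flag rate at p ≤ 0.05 is Φ(z − 1.96) + Φ(−z − 1.96).

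*No true interval effect, d = 1 month:*

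| s (months) | SSx + d²q | SE | GMT ratio | bias | z | formula | simulation |
|---|---|---|---|---|---|---|---|
| 0.6 | 668.7 | 0.0464 | 1.2 | 0.035 | 0.76 | 12% | 11% |
| 0.6 | 668.7 | 0.0464 | 1.3 | 0.051 | 1.10 | 20% | 20% |
| 0.6 | 668.7 | 0.0464 | 1.5 | 0.079 | 1.70 | 40% | 41% |
| 1.0 | 1626.1 | 0.0298 | 1.2 | 0.015 | 0.49 | 8% | 8% |
| 1.0 | 1626.1 | 0.0298 | 1.3 | 0.021 | 0.71 | 11% | 11% |
| 1.0 | 1626.1 | 0.0298 | 1.5 | 0.032 | 1.09 | 19% | 20% |

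With separate 9-15 and 16-19 indicators the simulated rate is about 5% throughout. With d = 0.5 month the formula gives 7%, 9% and 15% at s = 0.6, and 6%, 7% and 9% at s = 1.0.

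*True slope 0.15 ln per month, 9-15 interval 1 month shorter, ratio 1.3:*

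- s = 0.6, planned coding: mean slope 0.15 − 0.051 = 0.099; 0.099/0.0464 = 2.13, detection 57% (simulation 58%). Split coding: SE = 1.2/√538.6 = 0.0517; 0.15/0.0517 = 2.90, detection 83% (simulation 81%).
- s = 1.0: detection is about 99% with the planned coding and 99.9% with the split, so almost nothing is lost.

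**The same pooling in X3.** Take 455 as 228 (27-35) and 227 (36-45): q = 228 × 227/455 = 113.7. With ratio 1.3, d = 1 and s = 0.6, bias = 0.262 × 113.7/(538.6 + 113.7) = 0.046, SE = 1.2/√652.3 = 0.047 and z = 0.97, giving about 16% false flags. Splitting X1 alone does not remove this.

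**The case against.** The strongest reply is that the conditional problem may never arise. Delayed enrolment changes when most 9-15 girls start, not how their doses are spaced: the visit schedule and windows are the same for all (Sections 1.3 and 8.1.11.3). Only the first 25 have Dose 3 tied to the safety review, and their extra visit is scheduled for Day 77 against Day 184 for Dose 3. A reader might infer from Section 4.1.1 that these two strata are the ones most likely to differ in intervals; the documents do not show that. Nor do they show a titre difference. Section 9.9.1 assumes identical responses in 9-15, 9-19 and 20-26, though only as a power assumption, on which a diagnostic should not depend. All of this stands, and it limits the bias to a possibility.

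The size also depends on the assumed spread. Dose 3 may fall 155 to 364 days after Dose 1, so an SD above 0.6 month is possible, and the effect then shrinks. The table counts X5 alone, whereas the gate to Step 2 refers to X4 and X5 together. In the least favourable row at s = 0.6, a joint test is significant in about 30% of simulated trials, but both terms are individually significant in under 2%. The plan does not say which is meant.

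A reader might also infer that H4 is wholly unchecked, that its test is compromised, or that it is the only confirmatory test bearing on the indication sought. None of these holds. Girls aged 9-15 make up two thirds of the group behind X1. Table 3 marks the regression as supportive, so it alters no test. The indication sought also covers 27-45, to which H2 speaks.

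None of this supplies the missing 9-15 contrast, and that gap does not depend on the assumptions.

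**Conclusion.** The concern holds in two parts of unequal strength. First, on the text alone, H4 has no interval-adjusted contrast of its own, although the regression was added to examine exactly this threat to GMT-ratio comparisons. Second, pooling can bias X4 and X5, but only if 9-15 and 16-19 differ in both mean titre and mean interval. With a 1-month gap and ratios of 1.2 to 1.5, false X5 flags are about 11-41% at an interval SD of 0.6 month and 8-20% at 1.0 month, against about 5% with split indicators. Loss of detection is material only when interval spread is small (58% against 81% at SD 0.6; 99% against 99.9% at SD 1.0). These sizes rest on assumed inputs. The tests of H1 and H4, their alpha and their power do not change. This is an inexpensive improvement to a supportive analysis, not a flaw in the confirmatory plan.

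**What to change.** In the supportive regression:

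- Replace X1 by separate indicators for 9-15 and 16-19, and X3 by separate indicators for 27-35 and 36-45. In Step 2, give each its own interactions with X4 and X5.
- Report the interval-adjusted 9-15 vs 20-26 GMT ratio, with its confidence interval, at a common reference interval as the supportive counterpart of H4. The reference point matters once interactions are in the model.
- For the H1 counterpart, weight the 9-15 and 16-19 coefficients by the observed PPI numbers for each HPV type. A fixed 2:1 weighting would not match the group mean that H1 compares.
- State whether the gate to Step 2 is a joint test of X4 and X5 or requires each to be significant.

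Cost: Step 1 goes from 5 to 7 coefficients per HPV type. Step 2 goes from 9 to 15 (two more indicators, and eight interactions instead of four), with somewhat less precise interaction estimates. Age and dose dates are already collected. Because the analysis is not confirmatory, the change appears to fit the supplemental SAP route that Section 9 allows before database lock.

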1.3 Schedule of Activities (SoA)

Study Period	Stage I (Participants 9-45 years of age)										Stage II (Participants 9-19 years of age)					Notes
Visit Number/Title	Visit 1 Day 1	Visit 2 Day 9	Visit 3 Month h 1	Visit 4 Month h 2	Visit 5 Day 70	Visit 6 Month h 2.5*	Visit 7 Month h 3	Visit 8 Month h 6	Visit 9 Day 192	Visit 10 Month 7	Visit 11 Month 12	Visit 12 Month 24	Visit 13 Month 36	Visit 14 Month 48	Visit 15 Month 60	
Scheduled Day	1	9	32	62	70	77	93	184	8 days post Visit 8	31 days post Visit 8	183 days post Visit 8	548 days post Visit 8	913 days post Visit 8	1278 days post Visit 8	1643 days post Visit 8	
Scheduling Windows	± 0 day	8 to 14 days after Dose 1	31 to 38 days after Dose 1	40 to 82 days after Dose 1	8 to 14 days after Dose 2	15 to 17 days after Dose 2	31 to 38 days after Dose 2	155 to 364 days after Dose 1	8 to 14 days after Dose 3	21 to 49 days after Dose 3	± 28 days	± 28 days	± 28 days	± 28 days	± 28 days	
Administrative and General Procedures																
Informed Consent/ Assent	X															The interval between the date of consent/assent and the date of the Day 1 visit should be no more than 14 days apart. If the interval is 15 days or longer, then the participant must be re-consented.
Provide Participant Identification Card	X															
Assign Screening Number	X															
Review Inclusion/ Exclusion Criteria	X															

Study Period	Stage I (Participants 9-45 years of age)										Stage II (Participants 9-19 years of age)					Notes
Visit Number/Title	Visit 1 Day 1	Visit 2 Day 9	Visit 3 Month 1	Visit 4 Month 2	Visit 5 Day 70	Visit 6 Month 2.5*	Visit 7 Month 3	Visit 8 Month 6	Visit 9 Day 192	Visit 10 Month 7	Visit 11 Month 12	Visit 12 Month 24	Visit 13 Month 36	Visit 14 Month 48	Visit 15 Month 60	
Scheduled Day	1	9	32	62	70	77	93	184	8 days post Visit 8	31 days post Visit 8	183 days post Visit 8	548 days post Visit 8	913 days post Visit 8	1278 days post Visit 8	1643 days post Visit 8	
Scheduling Windows	± 0 day	8 to 14 days after Dose 1	31 to 38 days after Dose 1	40 to 82 days after Dose 1	8 to 14 days after Dose 2	15 to 17 days after Dose 2	31 to 38 days after Dose 2	155 to 364 days after Dose 1	8 to 14 days after Dose 3	21 to 49 days after Dose 3	± 28 days	± 28 days	± 28 days	± 28 days	± 28 days	
Review Medical History	X															
Record Medications and Non-study Vaccinations	X		X	X		X	X	X		X						
Physical Examination	X					X										Height and weight are only to be measured at Day 1.

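### The dosing-interval regression labels zero-month intercepts as age-group log-GMTs and never asks for the interval-adjusted GMT ratio it exists to examine

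*Combined protocol and SAP*

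**What the plan says.** Section 9.6.1 explains that wide vaccination windows may produce different dosing intervals, that the effect of intervals on titre may differ by age group, and that the GMT ratio could move as a result. A supportive analysis in the PPI population, run by HPV type, is meant to look into this.

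- **Step 1 model.** "A no-intercept regression model will be fitted on the natural logarithm of anti-HPV cLIA titers at 1 month post dose 3", on indicators for 9-19 (X1), 20-26 (X2) and 27-45 years (X3), plus "X4: Time (in months) from Dose 1 to Dose 2" and "X5: Time (in months) from Dose 2 to Dose 3". No centring or reference interval is given.
- **Stated meaning of the age coefficients.** "The regression coefficients associated with X1, X2, and X3 represent the expected GMTs in natural logarithm scale (or log-GMT") in each of the three age groups.
- **Step 1 outputs.** "The partial correlation coefficient associated with X4 and X5, given X1, X2, and X3 are already in the model, will be calculated and provided", together with nominal significance. Step 2 follows "If X4 and X5 are nominally statistically significant" at 0.05.
- **Step 2.** X1 and X3 are each interacted with X4 and X5. The outputs are again partial correlations and nominal p-values.

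Table 3 lists this as a supportive analysis by stepwise regression. Neither the text nor the table specifies an interval-adjusted GMT, an adjusted GMT ratio or a confidence interval from the model.

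**The concern.** There are two separate problems. First, the interpretation sentence does not describe the model as coded. With no intercept and raw months, an age coefficient is the fitted log titre when X4 and X5 are both zero, that is, with all three doses given at once. Anyone who exponentiates it and calls it a group GMT will be extrapolating.

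Second, the analysis is meant to show whether intervals shift the GMT ratio, but its listed outputs are about slopes. A significant slope does not show that the ratio moved, because that also requires the age groups to have different intervals. A non-significant slope does not bound the shift. The groups are not randomised, and Stage I is intended to support an extension of the indication. A reader of the report will want to see the H1 ratio with intervals held at the designated schedule, and the plan does not promise it.

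**Working it through.** **Inputs from the documents.** SD of log titre 1.2 and effective n of 586 (9-19) and 455 (20-26) from Section 9.9.1 and Table 6, and 455 (27-45) from Table 8; margin 0.67; one-sided alpha 0.0125; designated regimen 0, 2, 6 months, so X4 = 2 and X5 = 4. Windows (Sections 1.3 and 8.1.11.3): Dose 2 at 40 to 82 days and Dose 3 at 155 to 364 days after Dose 1, with at least 3 months between Doses 2 and 3.

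**Inputs that are assumed.** The slopes b4 and b5 per month, and the spread of the intervals. The documents give neither.

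**1. The plan's own figure.** There is none for the regression. For H1, SE = 1.2·√(1/586 + 1/455) = 0.0750 and -ln 0.67 = 0.4005. Power is 0.999 per type, and to the ninth power 0.991. Both match Table 6, so the SD and sample sizes are read correctly.

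**2. What the age coefficient is.** The model is E[Y] = b_g + b4·X4 + b5·X5. At the designated regimen the log-GMT of group g is b_g + 2·b4 + 4·b5. The coefficient b_g alone is the value at X4 = X5 = 0. The label is right only if 2·b4 + 4·b5 = 0.

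**3. Zero is outside the data.** The PPI population requires in-window vaccinations. Dose 1 to Dose 2 is then 40/30.44 = 1.3 to 82/30.44 = 2.7 months. Dose 2 to Dose 3 is at least 3 months; even from the day windows alone it is at least 155 - 82 = 73 days.

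**4. Size of the mislabelling.** Reading exp(b_g) as the GMT is wrong by the factor exp(-(2·b4 + 4·b5)):

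| Assumed b4, b5 (per month) | Factor |
|---|---|
| 0.05, 0.05 | 0.74 |
| 0, 0.10 | 0.67 |
| 0.10, 0.10 | 0.55 |
| 0.05, 0.20 | 0.41 |
| -0.05, -0.10 | 1.65 |

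**5. Precision of the coefficients, Step 1.** Assume interval SDs of 0.25 month (X4) and 0.8 month (X5), uncorrelated, with means of 2 and 4 in every group. The total n is 586 + 455 + 455 = 1496.
- Uncentred, 20-26 group: 1.2·√(1/455 + [4/0.0625 + 16/0.64]/1496) = 1.2·√(0.00220 + 89/1496) = 0.30.
- Centred: 1.2·√(1/455) = 0.056 (0.050 for 9-19).

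**6. The contrast b1 - b2.**
- Step 1: the slopes are common to all groups, so the origin cancels. The SE is 0.075 under either coding, and b1 - b2 is the interval-adjusted log GMT ratio.
- Step 2: each group has its own slopes, so the origin matters. Uncentred SE = 0.075·√(1 + 64 + 25) = 0.075·9.49 = 0.71; centred SE = 0.075. A 97.5% interval would run a factor of exp(2.24·0.71) = 4.9 either way uncentred, against exp(2.24·0.075) = 1.18 centred.

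**7. Why slope tests do not answer the question.** With common slopes, intervals move the unadjusted log ratio by b4·ΔX4 + b5·ΔX5, where Δ is the difference in mean interval between the two groups. The planned outputs do not report this quantity. With b5 = 0.10, a 0.5-month gap in the Dose 2 to Dose 3 interval gives exp(0.05) = 1.05; with no gap the shift is nil, however significant b5 is.

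**8. Simulation check.** Two thousand simulated trials used a true GMT of 500 in every group at 2 and 4 months, slopes of 0.05 and 0.10, interval SDs of 0.2 and 0.5 month, and a mean Dose 2 to Dose 3 interval of 4.5 months in 9-19 against 4.0 elsewhere. The 20-26 coefficient back-transformed to 308 uncentred (SE 0.405) and 500 centred (SE 0.056). The unadjusted ratio was 1.05, and the Step 1 adjusted ratio was 1.00 under both codings. The Step 2 contrast had SD 0.975 uncentred and 0.089 centred.

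**The case against.** The best defence is that nothing the plan commits to reporting from this model is altered. The partial correlations and p-values for X4 and X5 in Step 1, and for the interactions in Step 2, do not change with centring, so the decision to run Step 2 does not change either. The analysis is supportive. All of this stands, and it limits the point to a wrong sentence and a missing output.

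Some stronger readings are tempting but not supported:

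- **That the trial's reported GMTs would be wrong.** Section 9.6.1 defines the GMTs separately, as the antilog of the mean log titre, and Table 3 estimates them by ANOVA. The plan does not say that the regression coefficients will be reported as GMTs.
- **That the model cannot show whether H1 survives adjustment.** In Step 1 it can: b1 - b2 and its interval come straight from the fit. The plan just does not ask for them.
- **That the plan concedes bias toward the younger group.** The text is conditional: "If the shift in GMT ratio is in the direction greater than 1.0, the altered time interval between doses biased the hypothesis testing" in favour of the numerator group. It goes on to allow a shift below 1.0, with loss of power, or no meaningful shift.
- **That the distortion is known to be large.** Every magnitude rests on assumed slopes and intervals. At b5 = 0.10 a 1-month gap in mean interval would shift the ratio by 11% (exp(0.10) = 1.105), but the documents give no reason to expect a gap of that size.
- **That leaving out time from Dose 3 to the draw is an error.** Visit 10 falls "21 to 49 days after Dose 3", a 28-day spread, but this analysis concerns vaccination intervals and the PPI definition already enforces the Visit 10 window.

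**Conclusion.** The point holds in limited form. As coded, the X1 to X3 coefficients are zero-interval intercepts, and the sentence calling them age-group log-GMTs is wrong unless 2·b4 + 4·b5 happens to be zero. The planned outputs do not show whether intervals shifted the GMT ratio. Step 1 contains the answer but the plan does not extract it. In Step 2 the uncentred X1 minus X2 contrast is a poorly determined ratio at zero months, with an SE roughly nine times the centred one under the assumed interval SDs of 0.25 and 0.8 month. The algebra needs no assumptions; the sizes do. The confirmatory tests, the success criteria, the sample size and the ANOVA estimates are untouched. The change is still worth making, because the plan offers no other analysis of dosing-interval effects on the age comparison.

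**What to change.** 1. Define X4 as months from Dose 1 to Dose 2 minus 2, and X5 as months from Dose 2 to Dose 3 minus 4, in both steps. The age coefficients then are log-GMTs at the designated 0, 2, 6 schedule.
2. Reword the interpretation sentence to say so, naming the reference intervals.
3. For each HPV type, report the interval-adjusted GMT ratio for 9-19 versus 20-26 with its 97.5% CI, beside the primary ANOVA ratio and the 0.67 margin. If Step 2 is run, give the same contrast at 2 and 4 months. Label all of this supportive, with no effect on the H1 decision.
4. If a matching ratio is wanted for 9-15 versus 20-26 (H4), split X1 into 9-15 and 16-19 indicators; the model as written has no 9-15 term.
5. Optionally, add centred days from Dose 3 to the Visit 10 draw.

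The cost is a few lines of text and a reparameterisation of a model already planned, plus the extra indicator if item 4 is adopted. No new data are needed. The opening of Section 9 lets changes to non-confirmatory analyses be recorded in the supplemental SAP before final database lock.

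### The supportive dosing-interval analysis looks for age differences only if a pooled interval test is significant, and otherwise reads non-significance as no association, so its reassurance can be false

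*Combined protocol and SAP*

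**What the plan says.** Section 9.6.1 gives two reasons for the analysis. First, the extended windows may move titers away from what the 0, 2, 6 month schedule would give. Second, there is no guarantee that "the effect that the time interval between doses will have on anti-HPV titer read-outs will be the same in each of the age groups", so the GMT ratio between age groups could shift. To examine this, "a supportive analysis on PPI population will be performed by HPV type".

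Step 1 regresses log titer on three age-group indicators (X1 to X3), the Dose 1 to 2 interval (X4) and the Dose 2 to 3 interval (X5), with one slope per interval for all ages. "The nominal statistical significance of X4 and X5, given X1, X2, and X3 are already in the model, will be evaluated". The route to Step 2 opens with the condition "If X4 and X5 are nominally statistically significant" at the 0.05 level. If it is not met, "Step 2 outlined below will not be performed, and is an indication that there is no association between dosing interval and expected log-GMT".

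Step 2 adds X1*X4, X3*X4, X1*X5 and X3*X5, and the plan states its purpose: "These 4 explanatory variables provide insight on whether the effect of dosing interval varies by age group". No other part of the plan tests these terms. Table 3 lists only the stepwise models, and Section 9.11 adds only histograms of the actual intervals.

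**The concern.** A common-slope test is not a screen for an interaction. Step 1 estimates a weighted average of the three group slopes. If the groups respond in opposite directions the average can sit near zero, and if one group alone responds it is diluted. In both cases the gate may stay shut and the age-specific terms are never fitted. The plan then treats a p-value above 0.05 as pointing to no association, which a non-significant test cannot show.

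The gate is also not fully defined. It names X4 and X5 together without saying whether this means one joint test, both terms individually, or either term, and gives no outcome when only one is significant.

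At stake is the credibility of a robustness statement. Dose 3 may be given from 155 to 364 days after Dose 1 (Section 8.1.11.3), and this analysis is the plan's check on whether that spread disturbed the age comparison. A report that followed the rule exactly could say there was no sign of an interval effect without having looked at the age difference.

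**Working it through.** **The plan's own figure, to confirm n and SD.** Inputs from Section 9.9.1 and Table 6: effective n 586 and 455, SD of log titer 1.2, margin 0.67, one-sided alpha 0.0125.

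- SE = 1.2 × √(1/586 + 1/455) = 0.0750
- ln(1/0.67) = 0.4005, and 0.4005/0.0750 = 5.34
- Power = Φ(5.34 − 2.24) = Φ(3.10) = 0.999 per type. With the noncentral t it is 0.9990, and 0.991 over nine types.

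Both agree with Table 6. The stepwise analysis has no stated operating characteristics.

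**Inputs for the gate.** From the documents: n = 586/455/455 (Tables 6 and 8), N = 1496, σ = 1.2. Assumed, because the documents give no figure: the slopes b per month of Dose 2 to 3 interval for ages 9-19/20-26/27-45; the SD s of that interval (1 or 0.5 month around 4 months, equal across ages); no effect of the Dose 1 to 2 interval; a joint 2-df F test as the gate.

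**Formulas.**

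- Pooled slope: b̄ = Σ n·b / N
- Gate noncentrality (2 df): λ1 = N·s²·b̄²/σ²
- Interaction noncentrality (4 df): λ2 = s²·(Σ n·b² − N·b̄²)/σ²
- Significant interaction never examined ≈ (1 − gate probability) × interaction power, since the two numerators are independent.

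**Worked case, +0.2/−0.2/0, s = 1.** b̄ = (586 × 0.2 − 455 × 0.2)/1496 = 26.2/1496 = 0.0175. N·b̄² = 0.459, so λ1 = 0.459/1.44 = 0.32 and the gate opens in 7.5%. Σ n·b² = 0.04 × 1041 = 41.64, so λ2 = (41.64 − 0.459)/1.44 = 28.6 and interaction power is 99.6%.

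Setting Dose 2 to 3 intervals below the protocol's 3-month minimum to 3 months cuts an SD of 1 to 0.87 (s² = 0.75). Each range below runs from that limited case to the unlimited one.

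| Slopes (9-19/20-26/27-45) | λ1, λ2 at s = 1 | Gate opens | Interaction significant | Significant but never tested |
|---|---|---|---|---|
| +0.2/−0.2/0 | 0.32, 28.6 | 7% | 97-99.6% | 91-92% |
| 0/0/0.2 | 3.84, 8.79 | 31-40% | 51-65% | 35-39% |
| 0.2/0/0 | 6.38, 9.90 | 48-61% | 57-71% | 28-29% |
| 0.3/0.1/0.1 | 33.0, 9.90 | over 99% | 57-71% | under 1% |

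At s = 0.5 both λ fall to about a quarter. For +0.2/−0.2/0 the gate opens in about 6% and interaction power is 53-55%. For 0.3/0.1/0.1 the gate opens in 71-73% and interaction power is only about 20%, so roughly 5-6% of trials are affected.

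Simulation of the two-step rule with limited intervals (2,000 trials per scenario) agrees. The first three rows gave gate 6.6%, 31.1% and 49.6%, and missed interactions 91.2%, 34.7% and 28.8%.

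**Effect of the undefined gate.** In the same simulations, a common slope of 0.2 per month on the Dose 2 to 3 interval alone opened a joint gate in 99.9% of trials but a both-terms gate in 5.4%. With no interval effect at all, the joint, both-terms and either-term gates opened in 5.1%, 0.3% and 10.0%. The same data could therefore be reported in opposite ways.

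**The case against.** The strongest reply is that nothing confirmatory depends on this. The analysis is labelled supportive, its p-values are nominal, and H1 to H4 rest on the ANOVA and Miettinen-Nurminen tests. That stands, and it limits the severity.

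Step 1 also answers a question of its own, whether intervals matter at all, and the plan raises that one first. The text says "indication" rather than proof, and pooled partial correlations are reported whatever the p-value. These points are fair, but none of that output can show an age difference.

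The severe percentages belong to slopes that nearly cancel. The documents give no reason to expect opposite signs, and same-sign slopes pass the gate with little loss. When intervals vary little, the ungated test is weak too: +0.1/−0.1/0 at SD 0.5 gives it about 15% power. So the loss must be stated as a range.

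A reader might infer that the rule hides a bias in H1. The documents do not support that. A slope difference moves the GMT ratio away from its value at the nominal schedule only if mean intervals depart from that schedule. With mean departures d1 and d2 in months for ages 9-19 and 20-26, the log ratio shifts by b1·d1 − b2·d2. This is zero when both groups average the nominal interval, however different the slopes. No departure is stated or can be derived from the plan.

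**Conclusion.** The point holds as a weakness of a supportive analysis and should be corrected. The rule makes the age-by-interval question conditional on a pooled test that is nearly blind to opposing slopes and weakened for one-group effects, and it attaches a no-association reading to non-significance.

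With interval SD 1 month and a joint gate, the share of trials with a significant interaction that is never tested is about 91-92% for +0.2/−0.2/0, 28-39% for an effect of 0.2 in ages 9-19 or 27-45 alone, and under 1% for 0.3/0.1/0.1. These figures rest on assumed slopes and interval spread. The mechanism does not.

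It would go too far to conclude that H1 to H4 decisions or their type I error are compromised, or that age differences will generally be missed. Only the robustness reading is affected.

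**What to change.** - Delete the Step 1 gate and the no-association sentence.
- Fit the Step 2 model for all nine HPV types whatever Step 1 shows.
- Report the slope for each interval within each age group, with 95% CI.
- Centre X4 at 2 months and X5 at 4 months, so that the X1 minus X2 contrast is the log GMT ratio at the nominal 0, 2, 6 month schedule. Report that ratio with its CI beside the H1 result.
- Give one joint 4-df F test of the interactions per type, labelled nominal. If any Step 1 test is kept, say whether it is joint, both terms or either term.

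The cost is one more model per type on data already collected, with no change to alpha or conduct. As a non-confirmatory change before final database lock, it appears to fit the supplemental SAP route in Section 9.

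The downside is multiplicity. Nine ungated 5% tests would give 1 − 0.95⁹ = 37% chance of at least one spurious interaction if the types were independent. Interpretation should therefore rest on the estimates and intervals, not on counting p-values.
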